Study Title	A Multi-Center, Randomized, Open-Label Study to Evaluate Symptom Relief and Safety after Using Fexuprazan 40 Mg Compared to Esomeprazole 40 Mg in Patients with Gastroesophageal Reflux Disease (GERD).
Study center(s)	3 Study Center in Indonesia: 1. University of Indonesia Hospital 2. Islam Cempaka Putih Jakarta Hospital 3. Menteng Mitra Afia Jakarta Hospital
Study Period	
 Study duration: Approximately 14 months from IRB approval to completion Study duration for each subject: 8-12 weeks 
 - Screening period: Up to 2 weeks - Treatment period: Up to 4 weeks (unhealed subject will continue additional 4 weeks of treatment) - Follow-up period: For 2 weeks from the last dose
Indication	Gastroesophageal Reflux Disease (GERD) patients
Objective	To evaluate symptom relief and safety after using Fexuprazan 40 mg compared to Esomeprazole 40 mg for patient with Gastroesophageal Reflux Disease (GERD).
Number of subjects	134 subjects
Study Design	A Multi-Center, Randomized, Open label, Double-arm, Controlled study, Investigator Initiated Trial

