- The proportions (%) of subjects who have relieved from chronic cough for the first 7 days, full 4 weeks, and full 8 weeks after the first IP administration and its 95% confidence interval will be presented by treatment group. To compare the control group and study group, the 2-sided 95% confidence intervals and p-value will be obtained by using the Chi Square test or Fisher's Exact test method.
- The proportions (%) of subjects who have relieved from foreign body sensation for the first 7 days, full 4 weeks, and full 8 weeks after the first IP administration and its 95% confidence interval will be presented by treatment group. To compare the control group and study group, the 2-sided 95% confidence intervals and p-value will be obtained by using the Chi Square test or Fisher's Exact test method.

(Week 8 evaluation will only be applicable to patient receiving treatment 2)

[Safety Endpoints]

All adverse events (AEs) will be standardized according to MedDRA version 21.0 (or higher). The frequency and percentage of subjects with at least 1 AE (or adverse drug reaction) will be presented by treatment group, and the 95% confidence intervals will be also presented. The frequency and percentage of subjects who are withdrawn due to serious adverse events or AEs will be presented and the listings will be provided.

The descriptive statistics (mean, standard deviation, median, minimum, maximum, etc.) will be presented for continuous data, such as hematology, blood chemistry results, and vital signs by treatment group and visit; the frequency and percentage will be presented for categorical data, such as urinalysis and physical examination by category.

[Schedule of Study Activities]

	Screening (wash-out)	Treatment 1			Safety F/U ¹⁾	Treatment 2 (Unhealed Subject after 4 Weeks of Treatment)	Safety F/U ¹⁾	Withdrawal Visit ¹²⁾
Visit	Visit 1 ¹⁾	Visit 2	Visit 3	Visit 4	Visit 4-1	Visit 5	Visit 5-1	
Schedule	Day-14 ~	Day 0	Day 7	Day 28	Day 42	Day 56	Day 70	
Window	-	-	±3day	±5day	±5day	±5day	±5day	
Informed consent	O							
Demographic survey	O							
Assessment on symptom questionnaire (GERD-Q) ²⁾	O	O	O	O		O ¹³⁾		O ^{*)}
Quality of Life assessment (GERD-HRQL)		O	O	O		O ¹³⁾		O ^{*)}
Medical and surgical history ³⁾	O	O						
Prior/concomitant medications ⁴⁾	O	O	O	O	O	O	O	O ¹²⁾
Vital signs ⁵⁾	O	O	O	O	O ¹¹⁾	O ¹³⁾	O ¹¹⁾	O ¹²⁾
Physical examination	O	O	O	O	O ¹¹⁾	O ¹³⁾	O ¹¹⁾	O ¹²⁾
Laboratory tests ^{6),7)}	O			O	O ¹¹⁾	O ¹³⁾	O ¹¹⁾	O ¹²⁾
Pregnancy test ^{6),8)}	O	O						

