
The incidences of AEs and ADRs showed no statistically significant difference among treatment groups, and the events were all mild in severity and recovered without sequelae. One (1) case of moderate herpes zoster was reported as an SAE in the Esomeprazole 40 mg group, and no serious ADR, and AE and ADR resulting in death occurred during this study.

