1.6 Rationale for Selection of Doses

A dose-finding study in patients with erosive gastroesophageal reflux disease confirmed that the Fexuprazan 40 mg had a similar safety profile to the Esomeprazole 40 mg group, it was non-inferior to the Esomeprazole 40 mg group for the proportions of subjects with mucosal breaks completely healed by Week 8, primary efficacy endpoint, and at the same time, it had a significant improvement of symptoms compared to the Esomeprazole 40 mg group.

For the 'percentages (%) of subjects without the major symptoms for 7 days' and 'percentages (%) of subjects without the major symptoms during 8 weeks' after initiation of the IP administration, the effect of Fexuprazan 20 mg was similar to Esomeprazole 40 mg. The percentages (%) of subjects without the major symptoms for 7 days and 8 weeks in the Fexuprazan 40 mg group and the Fexuprazan 80 mg group tended to be higher than the Esomeprazole 40 mg group. Therefore, rapid improvement of symptoms is expected from the Fexuprazan 40 mg or higher which is deemed to be based on the advantage of Fexuprazan with APA mechanism in which activation of proton pump is unnecessary whereas the PPI takes 3 days or longer from the drug administration to the onset of action.

In addition, 'percentages (%) of days free of any major symptoms for 7 days' and 'percentages (%) of days free of any major symptoms for 8 weeks' tended to be higher in all Fexuprazan groups compared to the Esomeprazole 40 mg group. In particular, the Fexuprazan 40 mg group showed a statistically significant result compared to the Esomeprazole 40 mg group.

Percentages (%) of days free of each symptom for 7 days

[figure not shown]
Protocol No.DW_DWP1401262001

Protocol Version, 2.1

23 / 55 page

Version date 2024-06-19

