When the results were analyzed by dividing into daytime and nighttime, the percentages of daytime for 7 days were not significantly different between the Fexuprazan dose groups and the Esomeprazole 40 mg group. However, Fexuprazan 40 mg showed a statistically significant difference in nighttime heartburn and heartburn + acid regurgitation compared to the control group. Therefore, it is considered that the difference in the symptom improvement resulted from acid secretion inhibitory effects sustained until the nighttime with Fexuprazan 40 mg once daily dosing. Also, no significant difference was seen from the daytime results for 8 weeks compared to the Esomeprazole 40 mg group, except for heartburn symptom. However, the Fexuprazan 40 mg showed statistically significant difference in all nighttime symptoms (heartburn, acid regurgitation, heartburn + acid regurgitation) for 8 weeks compared to the Esomeprazole 40 mg. Therefore, it can be said that Fexuprazan 40 mg significantly improves the symptoms during the treatment period because it has a rapid onset of action compared to the control group and its acid secretion inhibitory effects last until the nighttime.

With this study, it is intended to develop an acid pump antagonist that can address the unmet medical needs of PPIs which are slow onset of action and nocturnal acid rebound. In the phase 2 study, the assessment of primary efficacy endpoint showed that all Fexuprazan groups were non-inferior to the control group and did not show difference among the dose groups, but it is expected that Fexuprazan 40 mg and higher dose would show difference in symptom improvement. Therefore, the phase 3 dose was set at Fexuprazan 40 mg to confirm the efficacy and safety in patients with erosive gastroesophageal reflux disease.

2 Study Objective

This study is to evaluate symptom relief after using Fexuprazan 40 mg compared to Esomeprazole 40 mg for patient with Gastroesophageal Reflux Disease (GERD).

3 Study Population

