9.2.4.1 Adverse events

AEs will be recorded based on worsening of existing symptoms or the newly occurring treatment-emergent adverse events (TEAEs) after administration of the IP.

For TEAEs, adverse drug reactions (ADRs), and serious adverse events (SAEs), descriptive statistics (number of subjects, incidence (%), and number of cases) will be presented, and Chi-square test or Fisher's exact test will be used for analysis depending on whether cells with the expected frequency of <5 is $>20\%$ or not.

AEs, ADRs, and SAEs will be coded by system organ class (SOC) and preferred term (PT) using the medical dictionary for regulatory activities (MedDRA) version 21.0 (or higher), and coded AEs will be presented with the number of subjects, incidence, and the number of cases by treatment group. The frequency and percentage of subjects who are withdrawn due to serious adverse events or AEs will be presented and the listings will be provided.

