9.2.4.2 Laboratory Tests, Vital Signs, and Physical Examination

The descriptive statistics (mean, standard deviation, median, minimum, maximum, etc.) will be presented for continuous data, such as hematology, blood chemistry results, and vital signs by treatment group and visit; the frequency and percentage will be presented for categorical data, such as urinalysis, physical examination by category.

For continuous variables, the paired t-test or Wilcoxon signed-rank test for intra-group tests for the difference between Predose (Visit 2 or Visit 1 if there is no Visit 2) and post dose will be conducted to compare the inter-visit differences. The two-sample t-test and Wilcoxon rank sum test will be carried out to compare the difference between the study group and the control group in the changes before and after administration.

For the categorical variables, the McNemar's test will be conducted for the intra-group change (Normal/NCS vs CS), and the Chi-square test or Fisher's exact test will be conducted for the inter-group difference.

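### Adverse events and categorical safety findings are compared between arms by chi-square/Fisher test only; a risk difference with its 95% interval should be added, because 67 per arm leaves these tests weak for drug reactions

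*Combined protocol and SAP*

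**What the plan says.** The study title sets out "to Evaluate Symptom Relief and Safety after Using Fexuprazan 40 Mg Compared to Esomeprazole 40 Mg", and the synopsis objective likewise pairs symptom relief with safety. Section 2 is narrower: "This study is to evaluate symptom relief after using Fexuprazan 40 mg compared to Esomeprazole 40 mg", with no mention of safety.

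For treatment-emergent adverse events (TEAEs), adverse drug reactions (ADRs) and serious adverse events (SAEs), Section 9.2.4.1 asks for subjects, incidence and number of cases. It then states that "Chi-square test or Fisher's exact test will be used for analysis depending on whether cells with the expected frequency of <5" make up more than 20% of cells. For categorical laboratory, vital-sign and examination findings, Section 9.2.4.2 says "the Chi-square test or Fisher's exact test will be conducted for the inter-group difference". Section 9.2.1 sets the default at two-sided 5%.

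The synopsis text on safety endpoints adds that subjects with at least one AE or ADR "will be presented by treatment group, and the 95% confidence intervals will be also presented". Those intervals describe each arm, and Section 9.2.4.1 does not repeat them.

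No section gives an interval for a between-arm safety difference, a safety margin, or a power or precision statement for safety. Section 9.4.2 sizes the trial on the efficacy endpoint alone.

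**The concern.** A test of zero difference answers a narrow question. When it does not reject, it leaves open how much excess harm the data still allow, and that is what a reader of a comparative safety objective wants to know. The plan handles its efficacy proportions differently: the primary endpoint is judged on a confidence bound for the difference (9.2.3.1, 9.3), and even the exploratory sleep, cough and throat comparisons are assigned a 95% interval as well as a p-value (9.2.3.3). The safety proportions get a p-value only.

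At stake is what the trial can say about comparative safety. If the tests have little chance of detecting a clinically relevant rise in drug reactions, a bare non-significant p-value could reassure more than the data allow. The primary efficacy conclusion is not affected.

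**Working it through.** **Inputs**
- Subjects per arm: 134 randomised 1:1 gives 67 (9.4.2). The safety set keeps everyone dosed at least once (9.1), so 67 is the maximum.
- Tests: two-sided 5%; Fisher if more than 20% of cells have an expected count below 5, otherwise Pearson chi-square (9.2.1, 9.2.4.1).
- Phase 2 rates, pooled over fexuprazan 20, 40 and 80 mg (13.8.1): ADR 13/156 = 8.3%; AE 36/156 = 23.1%.
- Comparator rate: **assumed**. The documents give no esomeprazole AE or ADR rate, so the ADR baseline is varied from 5% to 15%.

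**Step 1: the plan's own figure.** Pooled-variance non-inferiority Z-test with 0.885, 0.940, margin 0.10 and n = 53:
- Mean rate 0.9125; SE pooled = √(2 × 0.9125 × 0.0875 / 53) = 0.0549.
- SE unpooled = √((0.885 × 0.115 + 0.940 × 0.060) / 53) = 0.0546.
- Power = Φ((0.155 − 1.96 × 0.0549) / 0.0546) = 0.807, matching the stated 0.80729.
- 53 / 0.8 = 66.25, rounded up to 67 per arm, or 134 in total.

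The stated sample size is reproduced. It carries no information about safety.

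**Step 2: ADR comparison.** Power is the sum, over all pairs of counts (x₁, x₂) from two binomials with n = 67, of P(x₁)P(x₂) where the test chosen by the plan's rule gives p ≤ 0.05.

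| Assumed comparator ADR rate | Doubled rate | Power | Missed |
|---|---|---|---|
| 5% | 10% | 0.170 | 83% |
| 8.3% | 16.7% | 0.304 | 70% |
| 10% | 20% | 0.365 | 64% |
| 12.5% | 25% | 0.460 | 54% |
| 15% | 30% | 0.554 | 45% |

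Check on the 8.3% row by normal approximation: pooled SE = √(2 × 0.125 × 0.875 / 67) = 0.0571, unpooled SE = 0.0567, power = Φ((0.0833 − 1.96 × 0.0571) / 0.0567) = 0.307.

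**Step 3: TEAE comparison, assumed comparator 23.1%.**
- 1.5-fold rise to 34.6%: power 0.314, missed about 69%.
- Doubling to 46.2%: power 0.814, detected about 81%.

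**Step 4: what an interval would show.** Newcombe 95% interval for the difference, built from the Wilson limits of each arm:
- 6/67 vs 6/67: each rate is 0.0896 with Wilson limits 0.0417 and 0.1819. Half-width = √((0.0896 − 0.0417)² + (0.1819 − 0.0896)²) = 0.104, so the interval is −10.4 to +10.4 points.
- 11/67 vs 6/67: chi-square p = 0.19; interval −4 to +19 points.

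In the second case the p-value says only that the result is not significant. The interval says that an excess of nearly 20 points is not excluded.

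**The case against.** **No rule equates non-significance with similar safety.** A reader might infer that the plan will treat p > 0.05 as showing comparable safety. The documents do not support that. The only hypothesis and decision criterion concern efficacy (9.3, 9.4.2). The inference comes from the background on phase 2: Section 1.4 reports that "The incidences of AEs and ADRs showed no statistically significant difference among treatment groups", and Section 1.6 says the dose-finding study "confirmed that the Fexuprazan 40 mg had a similar safety profile to the Esomeprazole 40 mg group". Section 1.6 does not tie that phrase to a p-value, and Section 1.4 also relies on severity, recovery and SAEs. This stands: the misreading is a risk, not a planned step.

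**The tables allow the difference to be computed.** Counts, incidence by arm, coded events, AE withdrawals, listings and the synopsis's per-arm intervals are all planned, so it would be wrong to say that the p-value is the only safety result. It is the only inferential between-arm comparison specified for these categorical outcomes. Leaving the reader to derive the interval is a weak answer to a stated objective.

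**Low power for adverse events is normal in an efficacy trial of this size, and an interval adds none.** True. The case for the interval is that it displays the uncertainty.

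**The 8.3% baseline is soft.** It is a fexuprazan rate used for esomeprazole, pooled over three doses; 14 of the 24 ADR events listed in 13.8.1 came from 80 mg, which this trial does not use. This stands, and is why a range is given and no single miss rate is offered as the result.

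**Not every safety comparison is weak.** Also true: a doubling of TEAEs from 23.1% would usually be found, and continuous laboratory and vital-sign changes have their own two-sample tests. A general claim that the trial would fail to see any clear harm is not supported.

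**Section 2 omits safety.** It does, but the title and synopsis both name it.

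**Conclusion.** The point holds as a gap in the reporting of comparative safety. For TEAEs, ADRs, SAEs and categorical safety findings, the plan specifies a between-arm test but no between-arm estimate with an interval, although safety versus esomeprazole is an objective in the title and synopsis.

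The size depends on an unknown esomeprazole rate. A doubling of ADRs would be missed between 83% (5% baseline) and 45% (15% baseline) of the time, and about 70% at the phase 2 pooled fexuprazan rate. These figures assume all 67 per arm are in the safety set; fewer would make them worse. For TEAEs the weakness shows for a 1.5-fold rise but not for a doubling.

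The finding does not extend to the continuous safety comparisons or to the efficacy conclusion, and it is not a case for a larger trial.

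**What to change.** In Section 9.2.4.1, the categorical part of Section 9.2.4.2 and the synopsis, add the risk difference (fexuprazan minus esomeprazole) with a two-sided 95% confidence interval by the Newcombe or Miettinen-Nurminen method. Apply it to subjects with any TEAE, any ADR, any SAE, any AE leading to withdrawal, and any new clinically significant laboratory, vital-sign or examination finding.

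Add wording such as: A non-significant test will not be taken as evidence of comparable safety; comparative safety will be described from the estimated difference and its confidence interval.

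The p-values may stay, and the continuous comparisons need no change. The cost is protocol and SAP wording and a few table columns, with no additional patients, visits or data. The downside is that the intervals will be wide, about ±10 points for ADRs even at 6 against 6, so the safety statement will read less favourably than a bare non-significant p-value.

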9.2.4.2 Laboratory Tests, Vital Signs, and Physical Examination

The descriptive statistics (mean, standard deviation, median, minimum, maximum, etc.) will be presented for continuous data, such as hematology, blood chemistry results, and vital signs by treatment group and visit; the frequency and percentage will be presented for categorical data, such as urinalysis, physical examination by category.

For continuous variables, the paired t-test or Wilcoxon signed-rank test for intra-group tests for the difference between Predose (Visit 2 or Visit 1 if there is no Visit 2) and post dose will be conducted to compare the inter-visit differences. The two-sample t-test and Wilcoxon rank sum test will be carried out to compare the difference between the study group and the control group in the changes before and after administration.

For the categorical variables, the McNemar's test will be conducted for the intra-group change (Normal/NCS vs CS), and the Chi-square test or Fisher's exact test will be conducted for the inter-group difference.

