8.3.6 Vital signs

The followings will be measured in a seated position after resting for 5 minutes at the screening visit (Visit 1), Visit 2, and Visit 4. Any clinically significant abnormalities prior to the administration of the IP will be recorded in the medical history section, and any clinically significant abnormalities after the administration of the IP will be recorded in the adverse events section.

- Blood pressure (systolic/diastolic)
- Pulse rate
- Body temperature

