8.3.8 Laboratory tests

Laboratory tests will be conducted to check the inclusion/exclusion criteria and assess the safety (Visit 1, Visit 4, Visit 5, Withdrawal visit, and Safety F/U). At Visit 1, a re-test may also be conducted once according to the investigator's judgment and, in such a case, evaluation will be based on the results of re-test. Hepatitis testing will be conducted at the screening visit (Visit 1) only.

① Hematology	WBC with differential count (neutrophil, lymphocyte, monocyte, eosinophil, basophil), RBC, hemoglobin, hematocrit, platelets
② Blood Chemistry	Random blood glucose, ureum, uric acid, AST, ALT, creatinine, total bilirubin
③ Blood Coagulation test	PT, INR, APTT
④ Urinalysis	pH, specific gravity, albumin, bilirubin, glucose, urobilinogen, ketone, nitrite, occult blood, microscopy (urine RBC, urine WBC)

Any clinically significant abnormalities before and after the IP administration will be recorded as medical history and AEs, respectively.

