9.2 Statistical Analysis Method

9.2.1 General Principles of Result Analysis

The efficacy analysis will be conducted primarily on the PPS and FAS, and the PPS will be the primary analysis set.

In principle, all statistical analyses will use SAS® version 9.4 or higher and be performed with a two-sided test at a significance level of 5%, unless otherwise specified.

Descriptive statistics (mean, standard deviation, median, minimum, and maximum) will be calculated and provided for continuous variables, and the frequency and percentage will be provided for categorical variables.

The last observation carried forward (LOCF) method will be applied for correction of missing data of continuous endpoints among efficacy endpoints, and if the LOCF method cannot be applied, the raw data will be analyzed without correcting the missing data. However, the quality-of-life score (GERD-HRQL) will be analyzed using the raw data without applying the LOCF. For survival analysis, censoring will be utilized. When applying the LOCF, if the value immediately before the missing value is the baseline value, it will not be replaced.

The missing values of efficacy endpoints will be handled for both analyses on the FAS and PPS, and the safety endpoints will be analyzed with the raw data without replacing the missing values.

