- Descriptive statistics (mean, standard deviation, median, minimum, and maximum) of the proportions of days free of any heartburn, acid regurgitation, or heartburn/acid regurgitation for the first 7 days, full 4 weeks, and full 8 weeks from the first IP administration will be presented for daytime, nighttime, and daytime/nighttime by group. For comparison between treatment groups, an ANCOVA model will be applied with treatment group as a treatment effect. The results of ANCOVA model will be summarized as the LSM differences between the study group and the control group, the corresponding 2-sided 95% confidence interval, and p-value.
(Week 8 evaluation will only be applicable to patient receiving treatment 2)

3. Assessment on symptoms of reflux disease using GERD-Q

Descriptive statistics (mean, standard deviation, median, minimum, and maximum) for the changes from baseline in frequency at the first 7 days, 4 weeks, and 8 weeks will be presented by time point. For the changes from baseline in variables measured at the first 7 days, 4 weeks, and 8 weeks after the IP administration, an ANCOVA model including treatment group as treatment effect, and baseline value will be applied. The results of ANCOVA model will be summarized as the least squares mean (LSM) and standard error by treatment group, the LSM differences between the study group and the control group, the corresponding 2-sided 95% confidence interval, and p-value
(Week 8 evaluation will only be applicable to patient receiving treatment 2)

4. Quality of life assessment using GERD-HRQL

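### Between-arm changes in laboratory values and vital signs are tested without baseline adjustment, by two named tests with no rule between them and no estimate or interval

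*Combined protocol and SAP*

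**What the plan says.** Section 9.2.4.2 plans descriptive statistics by arm and visit for continuous laboratory results and vital signs. It then adds two layers of testing.

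- Within each arm: "the paired t-test or Wilcoxon signed-rank test for intra-group tests", applied to "the difference between Predose (Visit 2 or Visit 1 if there is no Visit 2) and post dose".
- Between arms: "The two-sample t-test and Wilcoxon rank sum test will be carried out to compare the difference between the study group and the control group", applied to the difference "in the changes before and after administration".

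No covariate is named for the between-arm comparison, and no estimate of the arm difference or interval is requested. The section does not say which of the two tests governs, or which post-dose visit is meant. Section 9.2.1 sets the general level: analyses are to "be performed with a two-sided test at a significance level of 5%, unless otherwise specified".

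Pre-dose values are scheduled. Section 8.3.8 has laboratory tests done to check eligibility and "assess the safety (Visit 1, Visit 4, Visit 5, Withdrawal visit, and Safety F/U"). Section 8.3.6 has vital signs measured "after resting for 5 minutes at the screening visit (Visit 1), Visit 2, and Visit 4", and the schedule table in Section 8.2 adds further post-dose visits.

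For efficacy changes the plan does adjust. For GERD-Q, Section 9.2.3.2, item 3, states: "an ANCOVA model including treatment group as treatment effect, and baseline value will be applied". Item 4 does the same for GERD-HRQL, with a further covariate. Both report an adjusted mean difference with a 95% CI.

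**The concern.** Safety compared with esomeprazole is part of the study title and of the synopsis objective. A reader of the laboratory and vital-sign tables will want to know how large a difference between the arms the data exclude. Test results on raw changes do not answer that question, and the raw change uses the pre-dose value inefficiently.

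There is also a reporting problem. If both tests are run and they disagree, the plan gives no basis for saying which one counts. The within-arm tests add a further risk, because a change that reaches significance in one arm and not in the other is easily read as a difference between drugs. Within one arm, a shift can come from washout between Visit 1 and dosing. For ALT, AST, total bilirubin, creatinine and BUN it can also come from regression to the mean, because values at or above twice the upper limit are excluded and one re-test may replace the first result.

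**Working it through.** **1. The plan's own figure.** The documents state no power or precision for the safety changes. Their only such figure is the primary sample size (Section 9.4.2): control rate 0.885, study rate 0.94, margin -0.1, one-sided 2.5%, pooled Z-test, 53 per group. The mean rate is (0.885 + 0.94)/2 = 0.9125.

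- Null SE = sqrt(2 x 0.9125 x 0.0875/53) = 0.0549.
- Alternative SE = sqrt((0.885 x 0.115 + 0.94 x 0.06)/53) = 0.0546.
- Power = Phi[(0.155 - 1.96 x 0.0549)/0.0546] = 0.807, which matches the stated 0.80729.
- 53/0.8 = 66.25, so 67 per arm and 134 in total, as stated.

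This figure concerns the binary primary endpoint and is not touched by what follows.

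**2. Change score against ANCOVA.** Let rho be the pre/post correlation, and take equal pre- and post-dose variances. Per subject, and ignoring the one degree of freedom spent on the slope:

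- change score: variance proportional to 2(1 - rho)
- ANCOVA: variance proportional to 1 - rho^2
- ratio: (1 - rho^2)/(2(1 - rho)) = (1 + rho)/2

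The documents give neither an SD nor a correlation, so rho is assumed over a range.

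| rho (assumed) | Variance ratio | Narrower CI, 1 - sqrt(ratio) | Equivalent extra subjects, 1/ratio - 1 | ANCOVA power where the change score has 80% |
|---|---|---|---|---|
| 0.3 | 0.65 | 19% | 54% | 93.5% |
| 0.5 | 0.75 | 13% | 33% | 89.9% |
| 0.7 | 0.85 | 8% | 18% | 86.0% |
| 0.9 | 0.95 | 3% | 5% | 82.0% |

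**3. Unequal variances.** With standard deviations s_pre and s_post, the change-score variance minus the ANCOVA variance is s_pre^2 + s_post^2 - 2 rho s_pre s_post - s_post^2(1 - rho^2) = (s_pre - rho s_post)^2, which is never negative. The direction therefore does not depend on equal variances; only the size does.

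**4. Two tests on the same data.** Simulation under no difference, with 20,000 data sets and 67 per arm, gave:

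| Distribution | Either test p < 0.05 | Verdicts differ |
|---|---|---|
| Normal | 6.1% | 2.0% |
| t with 3 df | 7.0% | 4.0% |
| Lognormal | 7.3% | 5.3% |

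The listed measurements come to 20 continuous laboratory analytes (10 haematology, 7 chemistry, 3 coagulation) and 4 vital signs (systolic and diastolic pressure, pulse, temperature). At one visit, a single test per parameter gives 24 x 0.05 = 1.2 expected false signals. Counting either test gives 24 x 0.061 = 1.5 to 24 x 0.073 = 1.8.

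**5. How the plan words the same choice elsewhere.** The within-arm sentence of Section 9.2.4.2, and Section 9.2.2 for demographic data, join the parametric and rank tests with *or*. Only the between-arm sentence uses *and*. Section 9.2.4.1 gives an explicit expected-count rule for Chi-square against Fisher. Neither 9.2.2 nor 9.2.4.2 gives a rule for t-test against Wilcoxon.

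**The case against.** The strongest reply is that this is a preference and not an error. A change-score comparison of randomised arms is valid, and ANCOVA is only more efficient. No hypothesis, margin or power attaches to these means, and Section 2 states the objective as symptom relief alone. Section 9.2.4 rests safety on adverse events and abnormalities; clinically significant laboratory and vital-sign changes are recorded as adverse events, and the arms are also compared on categorical classifications. All of that stands, and it limits the point to the supportive continuous summaries.

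The word *and* may be a slip for *or*. That is plausible, and it would remove the double testing in step 4 of the working. It would not remove the gap, because *or* with no selection rule leaves the choice open in an open-label trial.

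The gain rests on an unknown rho and is small if rho is high. This is correct: at 0.9 it is worth about 5% more subjects. But pre-dose laboratory values may come from Visit 1, up to 14 days before dosing, or from a test up to 2 weeks before that, so a correlation near 1 cannot be assumed.

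Washout and regression to the mean should act alike in both randomised arms, and the plan does include a direct between-arm test. That is right. The caution about those effects applies to the within-arm tests only.

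**Conclusion.** The point holds as a minor improvement. Section 9.2.4.2 uses a less precise comparison than the collected data allow, does not settle which test governs, and yields no between-arm estimate or interval. The direction of the precision loss is general. Its size, a variance ratio of 0.65 to 0.95, rests on an assumed rho of 0.3 to 0.9 and on equal pre- and post-dose variances.

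Four stronger readings are not supported:

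- A reader might infer that the safety comparison is biased. Under randomisation it is not.
- A reader might infer that the safety assessment as a whole loses precision. The adverse-event and abnormality analyses do not use these change scores, and the primary non-inferiority conclusion does not depend on them.
- A reader might infer that two competing p-values per parameter are certain. That follows only if *and* is meant literally.
- A reader might infer that every vital sign has a pre-dose value. The synopsis lists respiratory rate as a safety endpoint, but the vital-sign lists in the schedule footnotes and Section 8.3.6 do not include it. Likewise, the eligibility limit of twice the upper limit applies only to the five analytes named under concern, so regression to the mean from that source cannot be generalised to all parameters.

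**What to change.** In Section 9.2.4.2, for each continuous parameter with a recorded pre-dose value:

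- Make the between-arm analysis one pre-specified ANCOVA of the Week 4 (Visit 4) value on treatment and pre-dose value. Use the log scale where the distribution is skewed, and name those parameters before the data are analysed; the documents do not say which they are.
- Report the adjusted difference, or the ratio for log-scale parameters, with its 95% CI.
- Keep the Wilcoxon rank sum test on the change as a named sensitivity analysis.
- Summarise Visit 5, Withdrawal and Safety F/U values descriptively, along with any Visit 3 vital signs. Visit 5 covers only subjects who entered Treatment 2, a group selected after randomisation, and Safety F/U is a telephone contact with tests only if the investigator wants them.
- Label the within-arm paired tests descriptive and not a basis for conclusions about the difference between arms.

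The cost is a few sentences and routine programming. No new data, visits or subjects are needed.
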